3.3.3. Interruption or Discontinuation of Treatment

In accordance with legal requirements and ICH-GCP guidelines, every subject or his/her legal representative has the right to refuse further participation in the study at any time and without providing reasons (see also [Section 5.3](#)). A subject's participation is to be terminated

immediately upon his/her request. The Investigator should seek to obtain the reason and record this on the case report form (CRF).

If at the time of refusal a study product has already been administered, the subject should be advised on follow-up safety investigations. If a subject withdraws from the study, all efforts will be made to complete a final evaluation if possible. Subjects discontinued for having experienced an AE will be followed until the AE is resolved, a reasonable explanation is provided for the event, or the subject is referred to his/her own primary medical doctor (PMD). The specific AE in question will be recorded on the appropriate CRF.

If a subject develops a serious adverse event (SAE), his/her termination from the study will be considered by the Investigator. Similarly, if the subject develops conditions over the course of the study which would have excluded his/her entry in the study according to the safety-related medical exclusion criteria, he/she must be withdrawn immediately.

The subject may be withdrawn from the study at any time at the discretion of the Investigator for medical reasons and/or due to non-adherence to the treatment scheme and other duties stipulated in the study protocol. The reasons are to be documented on the CRF.

Individual patches may be discontinued if a reaction of a grade of 3 or greater (see [Section 3.5.5](#) for examples of values using additive grades from [Tables 3](#) and [Table 4](#)) occurs at any point during the study. Further patch applications of that product on that individual subject will be terminated. A “not patched” (NP) symbol and a score of 3 will be assigned for all subsequent days.

If a reaction is observed in any induction evaluation, a change in site location for the remaining applications in the Induction Phase will take place for that particular patch. See [Section 3.5.5](#) for interpretations of scores.

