Subjects who are absent once during the 3-week, 9-patch Induction Phase will be instructed to keep the patches in place and return to the facility on their next scheduled visit. They will be scheduled to receive a make-up (MU) patch application at the last Induction visit. The MU patches will be removed 48 – 72 (\pm 4) hours later and the sites will be graded. If subjects fail to return for removal/evaluation of the MU patch, a no ninth grading (N9G) will be recorded.

In cases where the subject misses the 9th evaluation in Induction Phase, the subject will be allowed to remove the patches by themselves in accordance with investigative personnel instructions. A telephone log will be written for any subjects that experience this situation to document the telephone conversation regarding the removal by subject.

Subjects who miss the 9th evaluation, but have had 9 patch applications will be considered to have completed the Induction Phase.

During Induction, the actual patch test grade is a combination of a numerical ([Table 3](#)) and letter ([Table 4](#)) grade consistent with the definitions given in the grading scales. A grade of 3 or higher to a specific study material (see [Section 3.5.5](#) for interpretation of symbols) observed at the first or second reading of the Induction Phase would indicate the subject is pre-sensitized, and application of the product(s) in question would be discontinued. If these reactions are observed after the first or second reading of the Induction Phase, this would necessitate a change in patch location to a naïve site. A second site change to the specific study material would potentially require a patch condition change to semi-occlusive conditions for the remaining applications in the Induction Phase (see [Section 3.5.6](#)).

Rest Period

During the Rest Period of approximately 10-14 days, subjects will not receive any application of study materials.

Challenge

At the Challenge Phase, subjects who have completed the Induction Phase and the Rest Period will have identical patches applied to naïve sites. Patches will remain on the naïve sites for 48 (\pm 1) hour to be evaluated at 30 (+ 10) minutes and 24 (\pm 1), 48 (\pm 1), and 72 (\pm 4) hours following patch removal (e.g., apply patch on Monday, remove patch on Wednesday, evaluate

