The actual patch test grades are a combination of a numerical ([Table 3](#)) and letter ([Table 4](#)) grades consistent with the definitions given in the grading scales. However, in order to determine discontinuation of a patch site (grade > 3) and to perform statistical analyses, grades containing letter grades have to be converted to numerical equivalents. These are converted as follows: A=0, C=1, E=2 and F, G, and H =3. These equivalents are considered additive to any numerical score (e.g., 2C=2+1=3), in this case the patch site would be discontinued.

Table 5: Other Notations

| Notation | Definition |
|----------|---|
| X | Subject absent |
| B | Burning or stinging sensation |
| PD | Patch dislodged |
| NA | Patch not applied |
| NP | No patch due to limiting irritation |
| I | Itching |
| D | Damage of the epidermis: oozing, crusting, and/or superficial erosions |
| p | Papular response |
| pv | Papulovesicular response |
| S | Spreading of reaction beyond patch site (i.e., reaction where study material did not come in contact with skin) |
| T | Tape related reaction |

Details regarding the statistical analysis of the cumulative irritation scores are provided in [Section 4.6](#).

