3.5.6. Criteria for Changing the Application Site or Conditions

A grade of 3 or higher to a study product (using [Table 3](#) and [Table 4](#)) observed at the first or second reading of the Induction Phase would indicate the subject to be pre-sensitized, and application of the product in question would be discontinued.

After the second reading of the Induction Phase, reactions graded 3 or higher (using [Table 3](#) or [Table 4](#)) require that the investigational product be applied to a naïve site under occlusive conditions. Such a change of application site may occur no more than twice during the Induction Phase for a particular product, after which applications of the product will be discontinued for that subject for the remainder of the study. Subjects requiring site changes due to irritancy in the Induction Phase will be considered evaluable for sensitization, provided that they receive a total of no fewer than 9 applications of the product.

No more than 2 changes for a given product will occur, whether the changes are to a new site under occlusive conditions (first move) or a new site under semi-occlusive conditions (second move).

Occlusive patch conditions include a Webril® cotton patch surrounded with Blenderm tape and covered with paper tape. There is no air flow under the patch. Semi-occlusive patch conditions include a Webril® cotton patch covered with paper tape, to allow air flow under the patch itself.

The 3-week period of continuous patch contact during the Induction Phase frequently results in tape-related irritation that is exacerbated by warm weather, but which occurs among some individuals irrespective of the season. Since adhesive tape is an integral part of the test article, tape-related irritation at the site will be documented as an application site reaction using the symbol “T” from [Table 5](#). Severe tape-related irritation will require a change of application site. Mild and moderate tape related reactions will not require of a change of application site. If all sites are experiencing tape reactions, the patch sites will be discontinued and a not patched (NP) symbol will be recorded for the remainder of the study. The subject will be discontinued from the study. An AE will be recorded in order to follow through to resolution of the tape related reaction.

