4.3. Subject Populations for Analysis

All subjects who receive treatment will be evaluable for AEs. The evaluation of sensitization will be based on all subjects who complete the Challenge Phase of the study. The analysis of cumulative irritancy will be based on all subjects who complete the Induction Phase of the study.

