4.6. Safety Evaluation

4.6.1. Cumulative Irritancy

Cumulative irritancy during Induction will be quantified by means of the cumulative irritancy index (CII), defined as the mean of the total cumulative irritation scores received during the Induction Phase (9 readings). The total cumulative irritation score for each subject and product will be calculated by summing each individual's scores on each of the 9 evaluation days in the Induction Phase. Response grades will be assigned numerical scores according to [Table 3](#) and [Table 4](#). Once the maximum score (combined score from [Table 3](#) and [Table 4](#)) or a 3 or greater is achieved, the remaining scores of 3 will be carried forward through all subsequent readings. No data imputations are to be made for discontinued subjects or missed evaluations.

The CII will be tested pairwise for product differences using Fisher's protected least significant differences in the context of the 2-way analysis of variance (ANOVA) including main effects of subject and product, without interaction. Pairwise differences will be tested for all products at the 5% level. Mean cumulative irritation scores will also be presented for each patch in a listing.

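### A reaction that the plan presumes allergic (grade 3 or more at Induction reading 1 or 2) enters the cumulative irritancy index as 24 to 27 points, with no separate code and no analysis without it

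*Combined protocol and SAP*

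**What the plan says.** - **Early reactions.** Section 3.5.1 says that a grade of 3 or more at the first or second Induction reading "would indicate the subject is pre-sensitized, and application of the product(s) in question would be discontinued". Section 3.5.6 repeats this: it "would indicate the subject to be pre-sensitized, and application of the product in question would be discontinued". Both stop the product, not the subject.
- **Scoring after a stop.** Under section 3.3.3, once a patch is stopped for a grade of 3 or more, NP is recorded and "a score of 3 will be assigned for all subsequent days". Table 5 in section 3.5.5.1 defines NP as "No patch due to limiting irritation".
- **Analysis.** Section 4.6.1 sums each subject's "scores on each of the 9 evaluation days in the Induction Phase" by product. Once a combined score of 3 or more is reached, "the remaining scores of 3 will be carried forward through all subsequent readings". It bars imputation for discontinued subjects and missed evaluations. Products are compared by a two-way ANOVA (subject, product) with Fisher's protected LSD at the 5% level.
- **Population.** Section 4.3: "The analysis of cumulative irritancy will be based on all subjects who complete the Induction Phase of the study".

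No section exempts a product stopped under the reading 1 or 2 rule from the carry-forward, and none plans an analysis without such products.

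**The concern.** The same event is presumed allergy in the conduct sections and near-maximal irritation in the analysis, although section 3.2 itself separates irritant from allergic reactions. After the stop nothing is observed at the site. The seven or eight later 3s are assigned, and they carry most of the total.

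The CII comparison is the only formal test in the plan. A few subjects allergic at entry could drive a significant difference between CCP-020 and vehicle, and it would be reported as irritation. The plan summarizes the reaction nowhere else. Sections 3.6.1 and 3.6.6 say that responses gradable on Tables 3 and 4 are not adverse events. Section 4.6.2 limits narratives to Challenge and Rechallenge. Section 3.5.1 assesses sensitization only in completed cases.

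**Working it through.** **The plan's own figure.** Section 4.2 gives a 95% upper bound of 1.5% for no reactions in 200 subjects. The exact one-sided bound is 1 − 0.05^(1/200) = 1.49%, so it reproduces. It concerns sensitization. The plan states no SD, power or expected score for the CII.

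**Inputs from the protocol.** 200 subjects (4.2), 3 products per subject (3.1), 9 readings summed, two-way ANOVA with LSD (4.6.1). Error df = 199 × 2 = 398. Tests are taken as two-sided.

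**Assumptions.** The background variability, the number k of such subjects, and that they count as Induction completers.

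**Points per subject**, with the stopping reading scored 3:
- reaction at reading 1: 9 × 3 = 27;
- reaction at reading 2: 8 × 3 + (0 to 2) = 24 to 26.

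**No background irritation.** If k subjects score v on CCP-020 and every other score is 0, v cancels:
- F = 199k/(200 − k) and LSD t = √(298.5k/(200 − k)).
- k = 2: F = 2.01, p = 0.135.
- k = 3: F = 597/197 = 3.03, p = 0.049; t = 2.13, p = 0.034; mean difference 3 × 27/200 = 0.405.

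The F is the same for v = 27, 24 or 3. This case therefore says nothing about the carry-forward.

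**With background variability.** For an assumed residual SD s of the 9-reading total:
- product mean square = k²v²/600;
- MSE = s² + (2/3)·k·v²·(1 − k/200)/398.

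Example with v = 27, s = 2, k = 5: MSE = 4 + 5.95 = 9.95, product mean square = 30.375, F = 3.05, just significant (5% critical value about 3.02). With k = 4: F = 19.44/8.79 = 2.21, not significant.

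Smallest k whose expected statistics are significant:

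| Assumed SD | 3s carried forward (27) | Only the observed 3 |
|---|---|---|
| 1 | 4 | 16 |
| 2 | 5 | 30 |
| 3 | 7 | 44 |

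At SD 4 and 5 with the 3s carried forward, k is 8 and 10.

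**Simulated chance of a significant CCP-020 excess with no true product difference** (overall F and LSD both p < 0.05):

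| Assumed background | k = 3 | k = 4 | k = 5 |
|---|---|---|---|
| Poisson totals with gamma subject effect, mean 1 | 28% | 60% | 88% |
| Same, mean 4, product total set to 27 | 14% | 23% | 40% |
| Same, mean 4, product total set to 24 | 12% | 19% | 32% |
| Normal, SD 1 | 28% | 65% | 90% |
| Normal, SD 2 | 15% | 32% | 50% |
| Normal, SD 3 | 8% | 19% | 30% |
| Normal, SD 4 | 7% | 11% | 20% |

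- The two mean-4 rows bracket a central range of about 13% to 35%.
- In the Poisson model the residual variance equals the mean, so mean 4 corresponds to SD 2. Its rates are lower than the SD 2 row because the 24 to 27 replaces the subject's own background total, leaving an excess of about 27 − 4 = 23.
- The normal rows were run against saline. Only CCP-020 is affected, so vehicle and saline are interchangeable.
- With only 3 points added at mean 1, the chance is about 4% to 7%. With these subjects removed it is about 1% to 2%, as with none.

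**Does section 4.3 remove them?** The text counts completion in different ways:
- by subject in 4.3, and in 3.5.1, where 9 patch applications complete Induction even if the ninth evaluation is missed;
- by product in 3.5.6, which asks for 9 applications of the product;
- by site in 3.4.7, where one dislodged patch makes that site incomplete. Section 3.6.6 keeps a subject in the study when one or two sites are stopped.

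If completion were judged by product, these subject-products would drop out and the effect would vanish. But then every product stopped during Induction would drop out as well, and the carry-forward rule would have little purpose.

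**The case against.** - **The plan may already exclude them.** A product stopped at reading 1 or 2 has had one or two applications, not nine. Section 3.3.3 also withdraws subjects who develop a condition matching a safety-related exclusion, and exclusion 7 covers known allergy to constituents. Withdrawn subjects would fall under the bar on imputation. This is arguable, but 3.5.1 and 3.5.6 stop only the product, and the bar does not mention a single stopped patch. What stands is that completion is unclear.
- **The label is a presumption.** This stands. A combined 3 can come from 2 plus C, or from fissured glazing alone, which are surface effects. A reader might infer that the plan declares such reactions not to be irritation; it only presumes allergy in order to stop patching.
- **The scenario is unsupported.** Distorting CCP-020 against vehicle needs allergy to the active alone. The documents give no rate for this. They exclude known allergy and report no treatment-related adverse events in the 17-patient Phase 2 study. An excipient allergy scores both ointments alike and distorts the comparison with saline instead.
- **Leaving out strong early reactions favors the product.** This stands against exclusion as the only analysis. Carrying 3s forward errs on the cautious side, so both analyses are needed.
- **Limited consequence.** Irritancy is not an objective in section 2, and sensitization is judged at Challenge and Rechallenge (4.6.2). This stands and limits the weight of the point.

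**Conclusion.** The scoring chain is explicit and the ambiguity in section 4.3 is real. A presumed allergic reaction adds 24 to 27 points to the CII. Under assumed variability, 3 to 5 such subjects in 200 who react to CCP-020 but not vehicle give a false significant difference in about 28% to 88% of trials at a mean total of 1, and about 13% to 35% at a mean of 4. Most of this comes from the carried-forward 3s. It rests on these subjects counting as completers and on an SD and a pre-sensitization rate that the documents do not give. At SD 3 to 5, 7 to 10 subjects are needed.

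Three stronger readings are not supported:
- That significance with 3 of 200 and no other irritation proves the carry-forward at fault. The F is identical without it.
- That the sensitization conclusion is biased. It does not use the CII.
- That subjects later classed as sensitized at Rechallenge should also leave the CII. That would discard scores observed in Induction because of a later result.

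**What to change.** In sections 3.3.3 and 4.6.1 and Table 5, and in the SAP promised in section 4.1:

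1. Give a product stopped under the reading 1 or 2 rule its own code, distinct from NP.
2. State whether such a subject counts as an Induction completer for the CII, and whether completion is judged by subject or by product.
3. Report the number of such stops by product.
4. Pre-specify the CII ANOVA twice: with the carried-forward 3s, and with these subject-products left out (the subject's other two products stay in the model). Call a significant product difference irritancy only if it holds in both.
5. Reconcile section 3.3.3, which ends further applications of a product after a grade of 3 or more at any point, with 3.5.1 and 3.5.6, which change the site for such reactions after the second reading. The scoring rule depends on which applies.

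The cost is one code, a few sentences and one extra table. The downside is that a truly irritant early reaction is absent from the second analysis, but it remains visible in the first.

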3.3.4. Withdrawals

The following medical and other reasons justify a premature termination (by subject of Investigator) of any of the study IPs.

- Adverse Event/Serious Adverse Event
- Death
- Protocol Violation (e.g. non-compliance)
- Investigator Judgment
- Pregnancy
- Lost to Follow-up

- Withdrawal by Subject
- Study Terminated by Sponsor
- Other

If a subject withdraws from the study, all efforts will be made to complete a final evaluation, if possible. Subjects discontinued for having experienced an AE will be followed until the AE is resolved, a reasonable explanation is provided for the event, or the subject is referred to his/her own primary medical doctor (PMD). The specific AE in question will be recorded on the appropriate CRF.

3.4. Treatments

3.4.1. Investigational Product and Controls

Investigational Product(s):

CCP-020 Topical Ointment

CCP-020 is a topical ointment, 1% (w/w). All excipients used in the topical formulation meet United States Pharmacopeia (USP)/ National Formulary (NF) criteria and are commonly used in ointment formulations. CCP-020 topical ointment is packaged in aluminum tubes, at 25 g/tube.

CCP-020 topical ointment and vehicle should be stored at room temperature (15°C/59°F to 30°C/86°F). The PI will be responsible for the suitable storage of the IPs in compliance with the storage instructions and must restrict access to the investigative personnel only.

Lot numbers will be given in the clinical study report.

Manufacturer:

TWi Pharmaceuticals will be responsible for the manufacturing and filling into the primary package; aluminum tubes. TWi Pharmaceuticals will be responsible to package and distribute to TKL. CCP will be responsible for final release of the product. TKL will be responsible for labeling the product upon site delivery.

The IPs will be dispensed via Eppendorf® Combitips onto separate occlusive patches at approximately 0.2 mL per patch applied 3 times weekly for 3 weeks (9 applications) during the Induction Phase, and one time at Challenge (10 times in total).

Control

A commercially available solution of 0.9% saline for topical administration (e.g., from Medline Industries Inc. (RDI30296)), applied 3 times weekly for 3 weeks (9 applications) during the Induction Phase, and one time at Challenge (10 times in total).

Eppendorf® Combitips will be used to apply 0.2 mL of the saline solution to its designated occlusive patch.

3.4.2. Description of Investigational Products

The IPs (CCP-020 [Diacerein 1%] topical ointment and vehicle) will be supplied in aluminum tubes for the clinical study. CCP-020 (Diacerein 1%) topical ointment and vehicle were manufactured and packaged in accordance with good manufacturing practice (GMP).

3.4.3. Description of Patch Conditions

CCP-020 (Diacerein 1%) topical ointment, vehicle, and negative irritant control will be evaluated under occlusive patch conditions by means of application to a 2 x 2 cm Webril® pad. The patches will be secured with nonporous Blenderm tape and hypoallergenic paper tape as needed.

3.4.4. Packaging/Labeling

The study medication tube label will show at least the following:

- Protocol number
- Storage conditions
- Instructions for use
- Expiration date
- Sponsor information
- Investigational drug warning
- Space to enter lot number.

A full product description can be found in the Investigator's Brochure (IB).¹

All study IPs should be stored at room temperature (15°C/59°F to 30°C/86°F).

3.4.5. Assignment to Treatment

3.4.5.1. Randomization

Each subject who signs an informed consent form (ICF) will be assigned a screening number. If the subject meets all of the inclusion and none of the exclusion criteria, and successfully completes the screening procedures, they will be enrolled in the study. Upon enrollment, each subject will be assigned a unique subject number and receive a randomization code, indicating application placement of the study materials. Each subject in this study will serve as his or her own control. All subjects will receive the IPs and control products at adjacent application sites.

The IPs (CCP-020 [Diacerein 1%] topical ointment and vehicle) and study control (saline) will be assigned in a randomized sequence to test Sites 1 through 3 using a set of independent 3-by-3 Latin squares. The same study material will be applied to the same test site throughout the study.

3.4.5.2. Blinding

The treatments (IPs and control) will not be blinded to investigative personnel involved in the preparation/application and removal of treatments.

Investigative personnel who are involved in the preparation/application and removal of the treatments will not perform the evaluation of skin responses. Investigative personnel who are involved in the preparation/application and removal of the treatments will be unblinded. The trained evaluator who will be evaluating skin responses will be blinded to IPs and control and the treatment allocation; however, because of the demarcations/skin coloration remaining on the skin following patch removal, complete blinding of the evaluators cannot be completely assured.

Investigative personnel, including the Investigator and trained evaluator involved in the evaluation of responses, will remain blinded during the course of the study until Database Lock and finalization of the Statistical Analysis Plan (SAP).

In the event of an emergency, if possible, the Investigator or designee will contact the Sponsor with notification of the intent to unblind the treatment codes prior to the actual unblinding. If it is not possible to notify the Sponsor prior to the unblinding, the Investigator or designee will contact the Sponsor immediately following the unblinding procedure and follow with a written notification to document the exact manner in which the code was broken and the justification for the unblinding. The Investigator will communicate the treatment identification to only the investigative personnel who require the information to manage the emergency. Unblinding will happen on site at TKL.

